5.4 Dose Modifications

Dose modifications are based on adverse events which are possibly, probably or definitely related to drug.

All toxicity grades below are described using the NCI Common Terminology Criteria for Adverse Events (CTCAE) version 4.0.

All appropriate treatment areas should have access to a copy of the CTCAE version 4.0. A copy of the CTCAE version 4.0 can be downloaded from the CTEP website (<http://ctep.cancer.gov>).

Lenalidomide Treatment Adjustment

See Table below for Lenalidomide Treatment Adjustment Steps

Lenalidomide (CC-5013) Treatment Adjustment Steps	
Starting Dose	25 mg daily for 21 days every 28 days
Dose Level -1	15 mg daily for 21 days every 28 days
Dose Level -2	10 mg daily for 21 days every 28 days
Dose Level -3	5 mg daily for 21 days every 28 days

Subjects experiencing \geq grade 3 adverse events will have their study drug held until resolution of the AE. Subjects experiencing grade 3/4 AEs prior to Day 15 of a cycle will need to hold lenalidomide. If AE improves to grade 1 or less prior to Day 21, lenalidomide should be restarted with a one dose level reduction for the remainder of the cycle. The next cycle will then continue with this reduced dose level. For grade 3 or 4 AEs which occur on or after Day 15 of a cycle, the subject's study drug is to be held for the remainder of the cycle and will be reduced by one dose level beginning with the next cycle. Once a subject's dose has been reduced, no dose-re-escalation is permitted.

Lenalidomide (CC-5013) Dose modifications based on adverse events (Arm A)

NCI CTC AE Grade	At retreatment* and Day 2-14 of Cycle	≥ Day 15 of Cycle
Sustained (≥ 7 days) Grade 3 neutropenia or ≥ Grade 3 neutropenia associated with fever (temperature ≥ 38.5° C) or Grade 4 neutropenia	Hold (interrupt dose) and follow CBC weekly. If the toxicity resolves to baseline or grade 1 prior to Day 21 restart at next lower dose level and continue the cycle until Day 21.	Omit lenalidomide for remainder of cycle. If toxicity resolves, restart lenalidomide next cycle with a decrease in dose by one dose level.
Thrombocytopenia ≥ Grade 3 (platelet count < 50,000/mm ³)	Hold (interrupt dose) and follow CBC weekly. If the toxicity resolves to baseline or grade 1 prior to Day 21 restart at next lower dose level and continue the cycle until Day 21.	Omit lenalidomide for remainder of cycle. If toxicity resolves, restart lenalidomide next cycle with a decrease in dose by one dose level.
Non-blistering rash Grade 2-3	Hold (interrupt) dose and follow. If the toxicity resolves to grade 1 prior to Day 21 restart at next lower dose level and continue the cycle until Day 21.	Omit lenalidomide for remainder of cycle. If toxicity resolves, restart lenalidomide next cycle with a decrease in dose by one dose level.
Grade 4	Discontinue lenalidomide and do not resume.	Discontinue lenalidomide and do not resume.
Desquamating (blistering) rash - any Grade	Discontinue lenalidomide.	Discontinue lenalidomide and do not resume.
Erythema multiforme ≥ Grade 3	Discontinue lenalidomide.	Discontinue lenalidomide and do not resume.
Sinus bradycardia/ other cardiac Arrhythmia Grade 2	Hold (interrupt) dose and follow. If the toxicity resolves to grade 1 prior to Day 21 restart at next lower dose level and continue the cycle until Day 21.	Omit lenalidomide for the remainder of the cycle. If toxicity resolves, restart lenalidomide next cycle with a decrease in dose by one dose level.
Grade 3-4	Discontinue lenalidomide.	Discontinue lenalidomide and do not resume.
Allergic reaction or Hypersensitivity Grade 2-3	Hold (interrupt) dose and follow. If the toxicity resolves to grade 1 prior to Day 21 restart at next lower dose level and continue the cycle until Day 21.	Omit lenalidomide for the remainder of the cycle. If toxicity resolves, restart lenalidomide next cycle with a decrease in dose by one dose level.
Grade 4	Discontinue lenalidomide.	Discontinue lenalidomide and do not resume.
Constipation Grade 1-2	Initiate bowel regimen and maintain dose level.	Initiate bowel regimen and maintain dose level.
≥ Grade 3	Hold (interrupt) dose and follow. If the toxicity resolves to grade 1 prior to Day 21 restart at next lower dose level and continue the cycle until Day 21.	Omit lenalidomide for the remainder of the cycle. If toxicity resolves, restart lenalidomide next cycle with a decrease in dose by one dose level.

Renal Function CrCl 30-60 mL/min	Hold (interrupt) dose and follow. If the toxicity resolves to < grade 1 prior to Day 21 restart at next lower dose level and continue the cycle until Day 21.	Omit lenalidomide for remainder of cycle. Reduce dose of lenalidomide by one dose level for next cycle.
CrCl <30 mL/min	Discontinue lenalidomide.	Discontinue lenalidomide.
Venous Thrombosis/embolism ≥ Grade 3	Hold (interrupt) dose and start anticoagulation; restart at investigator's discretion after adequate anticoagulation (maintain dose level).	Omit lenalidomide for remainder of cycle and start anticoagulation. Restart at investigator's discretion after adequate anticoagulation (maintain dose level).
Hepatic or other Non-hematologic toxicity Assessed as lenalidomide- Related ≥ Grade 3	Hold (interrupt) dose and follow. If the toxicity resolves to grade 1 prior to Day 21 restart at next lower dose level and continue the cycle until Day 21.	Omit lenalidomide for remainder of cycle.
Hyperthyroidism or Hypothyroidism	Omit lenalidomide for remainder of cycle, evaluate etiology, and initiate appropriate therapy. Restart lenalidomide next cycle (decrease dose by one dose level).	Omit lenalidomide for remainder of cycle, evaluate etiology, and initiate appropriate therapy. Restart lenalidomide next cycle (decrease dose by one dose level).

As noted in the table above, lenalidomide can be introduced after resolution of certain toxicities, midway through the cycle, provided the toxicity resolves prior to day 21. If drug needs to be held at the time of retreatment for adverse events, then the date of when treatment is resumed is considered day 1 of new treatment cycle. Patients requiring a treatment delay beyond 6 weeks will end protocol treatment.

If lenalidomide is held for an entire cycle and toxicity resolution does not occur within this time, lenalidomide dosing should be permanently stopped.

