3.1 Eligibility Criteria

_____ 3.1.1 Age \geq 18 years.

Rev. 12/13

_____ 3.1.2 Patients must be diagnosed with asymptomatic high-risk smoldering multiple myeloma (SMM) within the past 60 months, as confirmed by both of the following:

- 1) Bone marrow plasmacytosis with \geq 10% plasma cells or sheets of plasma cells at any time before initiating study treatment, including a marrow which must be obtained by bone marrow aspiration and/or biopsy within 4 weeks prior to randomization.

If plasmacytosis, % plasma cells: _____ Date: _____

If sheets of plasma cells, Date: _____

- 2) Abnormal serum free light chain ratio (< 0.26 or > 1.65) by serum FLC assay. FLC assay must be performed within 28 days of randomization.

Serum Free Light Chain Ratio _____ Date of Test _____

_____ 3.1.3 Patients must have measurable levels of monoclonal protein (M-protein): \geq 1g/dL on serum protein electrophoresis or \geq 200 mg of monoclonal protein on a 24 hour urine protein electrophoresis which must be obtained within 4 weeks prior to randomization.

Both SPEP and UPEP are required to be performed within 28 days prior to randomization.

Serum M-protein by SPEP _____ (g/dL) Date of Test: _____

Urine M-protein light chain excretion by UPEP _____(mg/24hr)

Date of Test: _____

NOTE: UPEP (on a 24-hour collection) is required, no substitute method is acceptable. Urine must be followed monthly if the baseline urine M-spike is ≥ 200 mg/24 hr. Please note that if both serum and urine M-components are present, both must be followed in order to evaluate response.

Rev. 7/14

- _____ 3.1.4 Patients must have no lytic lesions on skeletal surveys and no hypercalcemia (i.e., ≥ 11 mg/dL).
- _____ 3.1.5 The following laboratory levels must be obtained within four weeks prior to randomization:
 - _____ 3.1.5.1 Hemoglobin ≥ 11 g/dL.
Hemoglobin: _____ Date: _____
 - _____ 3.1.5.2 Platelet count $\geq 100,000$ cells/mm³.
Platelet: _____ Date: _____
 - _____ 3.1.5.3 Absolute neutrophil count ≥ 1500 cells/mm³.
ANC: _____ Date: _____
 - _____ 3.1.5.4 Calculated creatinine clearance ≥ 30 mL/min.
Creatinine clearance: _____ Date: _____
 - _____ 3.1.5.5 Bilirubin 1.5 mg/dL.
Bilirubin: _____ Date: _____
 - _____ 3.1.5.6 SGPT (ALT) and SGOT (AST) 2.5 times the upper limit of normal.
SGPT (ALT): _____ ULN: _____ Date: _____
SGOT (AST): _____ ULN: _____ Date: _____
- _____ 3.1.6 No prior or concurrent systemic or radiation therapy for the treatment of myeloma.

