5.1 Administration Schedule

5.1.1 Arm A Lenalidomide*

Lenalidomide 25 mg by mouth days 1-21 every 4 weeks (28 days).

Aspirin (or alternative prophylaxis) days 1-28 for each treatment cycle. Suggested dose is 325 mg/day, however the dose is at the discretion of the treating physician. Alternative dosing of 75mg/day or higher is acceptable provided the patient is at low risk of thrombosis.

All patients on Arm A are required to receive prophylaxis against thrombosis. For patients in Arm A, physicians should consider prophylaxis with aspirin alone as studies with single agent lenalidomide in the setting of relapsed disease show a relatively low incidence of thrombosis (< 5%). See Section [5.5.2.1](#) for acceptable alternative prophylaxis.

Treatment continues until progression to symptomatic myeloma or discontinuation due to toxicity.

For patients with CrCl 30-60 mL per minute, lenalidomide dose is 10 mg per day for days 1-21 every 28 days. Creatinine clearance (CLcr) can either be measured CLcr or estimated by the Cockcroft-Gault method: $\{[140 - \text{age (yrs)}] \times [\text{lesser of IBW (kg) or actual weight (kg)}]\} / [72 \times \text{serum creatinine (mg/dL)}]$; multiply by another factor of 0.85 if female.

* **NOTE:** The first 44 patients to accrue will be placed on Arm A without randomization (Phase II).

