7.1 Therapeutic Parameters (for both arms of the study)

1. Prestudy scans and x-rays used to assess all measurable or non-measurable sites of disease must be done within **4 weeks** (28 days) prior to randomization/registration.
2. Prestudy CBC (with differential and platelet count) should be done **4 weeks** (28 days) before randomization/registration.
3. All required prestudy chemistries, as outlined in Section 3, should be done **4 weeks** (28 days) before randomization/registration unless specifically required on Day 1 as per protocol.

Rev. 8/11

Procedure	Prior to registration (≤ 28 days) ¹	10-14 days prior to starting Treatment or Observation	< 24 hours prior to starting Treatment or Observation	Induction- At the end of each Treatment or Observation cycle	Day 1 of each cycle	Studies needed to confirm sCR or CR	Periodically during Treatment or Observation	At study discontinuation or progression (whichever comes first)	28 Days after discontinuation of treatment	Post treatment to 10 years from study entry ¹¹
History and exam ⁶	X			X				X		X
Bone Marrow Aspirate and Biopsy ⁹	X					X				
ECOG Performance Status	X			X				X		X
NYHA Classification	X									
Chemistry labs ³	X			X				X		X
CBC with differential ⁴	X			X				X		X
Serum light chain assay	X			X		X		X		X
Serum immunoglobulin G, A, M	X			X				X		X
QOL ⁷	X			X				X		X

	SPEP	X			X				X		X
	Serum M-protein immunofixation	X					X				
	24 hr UPEP	X			X ^{2,10}				X ^{2,10}		X ^{2,10}
	Urine M-protein immunofixation	X					X				
	Metastatic bone survey	X						X ¹²	X		X ¹²
	ECG (12-lead)	X									
	Serum Pregnancy test for FCBP ⁵	X	X ⁵	X ⁵	X ⁵				X ⁵	X ⁵	
Rev. 8/11	Patient Education and Counseling ¹⁴	X		X	X	X			X	X	
	Serum Beta-2 microglobulin	X							X		
	C-reactive protein	X									
	LDH	X									
Rev. 8/11	Dispense lenalidomide ¹⁵			X		X					
Rev. 7/14	TSH (ARM A ONLY) ¹⁶	X									X ¹³
	Ultrasound ⁸				X						
	Documentation of oral drug				X						
	MRI (spine and pelvis)	X									
Rev. 12/13	Biological Sample Submissions	See Section 7.2									

1. Registration test results can be used for cycle 1 if less than 7 days before starting cycle 1.

-

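### For a drug-related fall in creatinine clearance to 30-60 mL/min in a patient on 25 mg, Section 5.4 from Day 15 gives 15 mg where Section 5.1.1 gives 10 mg, and nothing says which rule governs

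*Combined protocol and SAP*

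**What the plan says.** Section 3.1.5.4 admits patients with "Calculated creatinine clearance ≥ 30 mL/min", so a clearance of 30-60 is acceptable at entry. Section 5.1.1 then gives the dose: "For patients with CrCl 30-60 mL per minute, lenalidomide dose is 10 mg per day for days 1-21 every 28 days". It does not restrict this to the starting dose or to baseline renal function.

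Section 5.4 limits its own scope: "Dose modifications are based on adverse events which are possibly, probably or definitely related to drug". Its step table runs 25, 15, 10, 5 mg. Its renal row for CrCl 30-60 has two columns:

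- **On or after Day 15:** "Omit lenalidomide for remainder of cycle. Reduce dose of lenalidomide by one dose level for next cycle".
- **At retreatment or Day 2-14:** hold the drug and follow. The release is "If the toxicity resolves to < grade 1 prior to Day 21 restart at next lower dose level".

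Below 30 mL/min, both columns discontinue the drug. After the table, Section 5.4 adds: "If lenalidomide is held for an entire cycle and toxicity resolution does not occur within this time, lenalidomide dosing should be permanently stopped". It also ends protocol treatment when a delay exceeds 6 weeks. Reductions are one-way: once the "dose has been reduced, no dose-re-escalation is permitted".

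**The concern.** The protocol accepts a clearance of 30-60 mL/min and names a dose for it. A patient on 25 mg whose clearance falls into that range because of the drug can be given a higher dose than that, depending on which section the site follows. Sections 5.1.1 and 5.4 do not refer to each other. At stake is the exposure of asymptomatic patients with reduced clearance on a drug given until progression or toxicity, and consistency between sites in applying the rule.

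**Working it through.** **Inputs.** From 5.1.1: 10 mg at CrCl 30-60, 21 dosing days per cycle. From 5.4: levels 25, 15, 10 and 5 mg, and one level down from Day 15.

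**Dose per cycle** = daily dose × 21.

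- 25 mg: 25 × 21 = 525 mg
- 15 mg: 15 × 21 = 315 mg
- 10 mg: 10 × 21 = 210 mg
- 5 mg: 5 × 21 = 105 mg

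**Size of the conflict from 25 mg.** 315 − 210 = 105 mg more per cycle, and 315 / 210 = 1.50, so the 5.4 dose is 50% above the 5.1.1 dose. 10 mg is two levels below 25 mg, so a single step cannot reach it.

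**Who is affected.** The last column is the lower of 10 mg and the next level down.

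| Dose when the fall is found | 5.4 from Day 15, as written | 5.1.1 | Lower of 10 mg and one level down |
|---|---|---|---|
| 25 mg | 15 mg | 10 mg | 10 mg |
| 15 mg | 10 mg | 10 mg | 10 mg |
| 10 mg | 5 mg | 10 mg | 5 mg |
| 5 mg | no lower level defined | 10 mg | no lower level defined |

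Only on 25 mg does 5.4 give more than the 5.1.1 dose.

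**Is recovery required before the 15 mg dose?** Not in this row. Most other hold-and-restart rows make the next-cycle restart in the Day 15 column conditional on the toxicity resolving; the renal row does not. The text before the table does hold drug until resolution for events of grade 3 or higher. The documents do not say what grade a CrCl of 30-60 carries, so that text cannot be relied on to close the gap.

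**Do the two columns agree?** Take a clearance that falls to 30-60 after Day 15 and stays there. The Day 15 column reduces the dose and continues next cycle. If the value is unchanged on the next Day 1, the retreatment column says hold. Section 7.1 schedules chemistry, which includes creatinine clearance, under the heading "Induction- At the end of each Treatment or Observation cycle". The same sample can therefore be read as a late-cycle finding or as the retreatment check.

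**The case against.** The strongest reply is that the two sections have different scopes. Section 5.1.1 is the administration schedule; 5.4 handles drug-related injury. A patient who enters at 30-60 and one brought there by the drug are different clinical cases, and treating them differently is a legitimate choice. That is possible, but the text does not say it. It would also mean that the patient with drug-related decline gets 15 mg at a clearance where another patient starts on 10 mg.

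A second reply is that if 5.1.1 applies throughout treatment, it works as a ceiling, and a site applying both sections gives 10 mg. This reading stands as possible too. It shows that 15 mg is not a settled instruction: the excess arises when a site follows 5.4 as written without looking back to 5.1.1. The ceiling is not stated, however, and stating it is the remedy proposed.

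A reader might also infer some stronger points that the documents do not support:

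- **That a stable 30-60 can never be released from the hold, and so always ends in a permanent stop.** The release is a CTCAE grade, and the documents do not give the cut-offs. A hold could still serve to watch for a fall below 30 even if an unchanged value met the release.
- **That 15 mg is the routine outcome because chemistry is drawn at cycle end.** Dosing ends on Day 21, so by then little or nothing is left to omit, and the value naturally informs the retreatment decision, where the row says hold.
- **That a number of affected patients can be given.** The nearest entry is acute kidney injury in the rare (<3%) column of the Section 5.3 adverse event list, which is a different event. Any count would also have to include the 44 phase II patients as well as the 90 planned on the randomized lenalidomide arm.

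**Conclusion.** The inconsistency is real and narrow. For a drug-related fall in CrCl to 30-60 mL/min in a patient on 25 mg, found on or after Day 15, Section 5.4 as written leads to 15 mg while 5.1.1 gives 10 mg, a 50% difference per cycle with no precedence rule. The two columns of the renal row can also give different instructions for the same persistent value; whether a stable 30-60 satisfies the hold's release cannot be settled from the documents.

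The conclusion rests on reading 5.1.1 as it stands, without an implied restriction to baseline. If it is only a starting-dose rule, the direct contradiction goes, but the unexplained difference in dose at the same clearance remains. Frequency is unknown and probability of harm is not estimated. Endpoints, sample size and the primary analysis are not in question.

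**What to change.** Add one sentence to the renal row of the 5.4 table, in both columns: *While CrCl remains 30-60 mL/min, any restart or next-cycle dose is one dose level below the current dose or 10 mg (as in 5.1.1), whichever is lower.* Here the current dose means the dose in use when the fall was found, so the reduction is made once per event.

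Leave unchanged the existing hold, the stop after an entire cycle on hold, the 6-week limit and the rule for CrCl below 30. The sentence sets the dose when a restart occurs; it does not decide whether a stable 30-60 counts as resolved. Whether patients with persistent drug-related decline should stay on drug, and after what evidence of stability, is for the clinical team.

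Cost: one table row, with an addendum, IRB review and clinical sign-off because it sets a dose. Some patients on 25 mg will get 10 mg instead of 15 mg, a cut of 1 − 210/315 = 33% per cycle, and the bar on re-escalation makes that lasting. The rule never raises a dose, and the supplied 5 mg capsules already allow 10 mg.

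### Arm A instructions conflict on lenalidomide after an on-treatment fall of CrCl to 30-60 mL/min and on confirmed pregnancy, with a minor aspirin query; the sponsor must reconcile them

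*Combined protocol and SAP*

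**What the plan says.** **Renal function.** Section 5.1.1 states: "For patients with CrCl 30-60 mL per minute, lenalidomide dose is 10 mg per day for days 1-21 every 28 days". Nothing in that sentence confines it to Cycle 1 or to baseline CrCl. The Section 5.4 table has a row for the same CrCl range, with two cells:

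- At retreatment and on Days 2-14, drug is held, and then: "If the toxicity resolves to < grade 1 prior to Day 21 restart at next lower dose level".
- On or after Day 15, drug is withheld for the rest of the cycle, and then: "Reduce dose of lenalidomide by one dose level for next cycle".

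The step table puts one level below 25 mg at "15 mg daily for 21 days every 28 days". Text after the table treats the day drug is resumed, after a hold at retreatment, as Day 1 of the new cycle. It ends protocol treatment if the delay exceeds 6 weeks, and adds: "If lenalidomide is held for an entire cycle and toxicity resolution does not occur within this time, lenalidomide dosing should be permanently stopped". Section 5.4 opens with a scope sentence: "Dose modifications are based on adverse events which are possibly, probably or definitely related to drug".

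**Pregnancy.** Section 8.1.8 and Appendix VI require lenalidomide to be stopped at once in a pregnant patient, and the Appendix VII counseling text tells her to stop. Appendix XIII leaves the question of her continuing protocol treatment to the site physician, the study chair and the operations office. For a male patient's pregnant partner, Section 8.1.8 also requires discontinuation, whereas Appendices VI and VII mention only notification.

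**Aspirin.** Sections 5.1.1 and 5.5.2.1 make thrombosis prophylaxis mandatory in Arm A. The Section 5.5.2.1 table allows 0 to 81 mg of aspirin for patients who cannot tolerate 325 mg. That entry sits in the alternative-prophylaxis column, whose footnote rules out aspirin alongside alternative prophylaxis.

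**The concern.** Two sites that each follow current protocol text could manage the same Arm A patient differently on a safety rule. In the renal case the choice persists, because Section 5.4 bars re-escalation once a dose has been reduced. The situation is also one the schedule is built to detect: Section 7.1 calls for chemistry, including creatinine clearance, at the end of each cycle, so a fall may well be found on or after Day 15 or at retreatment. In the pregnancy case, one appendix leaves open something that the drug section and two other appendices close. At stake is consistent patient management, not the statistical design.

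**Working it through.** **1. Renal: inputs**
- Dose steps (Section 5.4): 25 → 15 → 10 → 5 mg, each for 21 days of a 28-day cycle.
- Dose for CrCl 30-60 (Section 5.1.1): 10 mg for 21 days.
- Case: a patient on 25 mg whose CrCl falls to 30-60 on Day 15 or later, with the fall judged at least possibly drug-related (so that Section 5.4 applies), and who stays in that range.

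| Text followed | Next-cycle instruction | Amount per cycle |
|---|---|---|
| 5.1.1 | 10 mg (two steps below 25 mg) | 10 × 21 = 210 mg |
| 5.4, Day 15+ cell | 15 mg (one step below 25 mg) | 15 × 21 = 315 mg |
| 5.4, retreatment cell | Hold pending resolution | None: the start of the cycle is delayed |

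The ratio of the two doses is 315 / 210 = 1.5. The two dose rules agree only for a patient who is on 15 mg when the row is applied (one step down is then 10 mg).

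**2. Renal: what a continued hold leads to.** Two sentences in Section 5.4 can end treatment. One acts on a delay beyond 6 weeks (6 × 7 = 42 days). The other acts when drug is held for an entire cycle without resolution, which is 28 days if a cycle is counted at its nominal length. The text does not say which applies first, or how either relates to the Day 15+ cell, which has already set a dose for the next cycle.

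**3. Pregnancy: passages side by side**

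| Place | Instruction for a pregnant patient |
|---|---|
| 8.1.8 | Stop drug immediately |
| Appendix VI | Stop drug immediately; also stop while a missed period or abnormal test is evaluated |
| Appendix VII | Patient told to stop; dispensing blocked if pregnant |
| 8.1 note | Negative test needed before dispensing (if applicable); at most a 28-day supply |
| Appendix XIII | Continuation decided case by case |

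Appendix VI already covers the suspected case by stopping drug during evaluation. Once pregnancy is confirmed, the three stop instructions and Appendix XIII cannot all be followed if the case-by-case decision is to continue. The dispensing checks limit the practical exposure mainly to drug already in hand: at most one cycle, or 21 daily doses.

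**4. Aspirin.** Zero aspirin together with another listed agent is compatible with mandatory prophylaxis. Zero aspirin with no other agent is no prophylaxis, and conflicts with it. A nonzero dose from the same entry is aspirin listed under alternative prophylaxis, in a column whose footnote excludes aspirin.

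**The case against.** The best defence on the renal point is that Section 5.1.1 belongs to the administration schedule and sets the starting dose, while Section 5.4 handles events on treatment. That is coherent and may be what was meant. But Section 5.1.1 does not say so. Even if it did, the Day 15+ cell and the retreatment cell would still need to be put in order for a patient whose CrCl stays at 30-60.

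On pregnancy, Appendix XIII also covers suspected pregnancies and inconclusive tests, so a decision about continuing makes sense once pregnancy has been excluded. That part stands and confines the conflict to confirmed pregnancy. The male-partner difference is an alignment gap, since a site could both notify and stop.

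Some stronger readings are tempting but not supported:

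- *The hold produces a cycle with no drug.* Under Section 5.4 the resumption day starts the new cycle, so the hold is a delay that may end treatment.
- *A patient who enters at CrCl 30-60 on 10 mg is forced further down.* Section 3.1.5.4 admits such patients, but the scope sentence limits Section 5.4 to drug-related events, and a stable baseline value is not one.
- *The renal row is anomalous beside the other rows.* Its Day 15+ cell lacks the condition "If toxicity resolves, restart lenalidomide next cycle with a decrease in dose by one dose level", but so do the thrombosis, hepatic/other and thyroid cells. The allowance "If the toxicity resolves to baseline or grade 1 prior to Day 21 restart at next lower dose level" appears only in the neutropenia and thrombocytopenia rows. Neither absence shows much.
- *75 mg is a minimum aspirin dose.* The schema and Sections 5.1.1 and 5.5.2.1 leave the dose to the physician and describe 75 mg or more as acceptable at low thrombotic risk. That is not a floor.

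The 0 in the aspirin entry may itself be a typing or PDF-reading slip.

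**Conclusion.** Two conflicts in current text hold, with high confidence.

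1. **Renal (main point).** For a patient on 25 mg with a persistent fall of CrCl to 30-60 first seen on Day 15 or later, the plan gives both 210 mg and 315 mg for the next cycle. A separate instruction in the same renal row would hold drug at retreatment and could end treatment. This assumes the fall is judged at least possibly drug-related; otherwise the scope sentence takes it out of Section 5.4.
2. **Pregnancy.** For confirmed pregnancy, three places stop drug and one leaves continuation open.

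The aspirin entry is minor, with low to medium confidence. It conflicts with mandatory prophylaxis only if 0 mg is given with no other agent, and it depends on the source PDF reading as printed here.

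The number of patients affected cannot be derived from the documents, and none is estimated. Alpha, power, the event count and the intention-to-treat analysis do not change. The passages should be reconciled; which dose or rule is right is for the sponsor to decide.

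**What to change.** - **Renal.** State which of Section 5.1.1 and the Section 5.4 renal row governs the starting dose, and which an on-treatment fall. State how the Day 15+ cell, the retreatment cell and the two end-of-treatment sentences work together when CrCl stays at 30-60. Add one sentence confirming whether the row applies to patients who entered in that range.
- **Pregnancy.** Reconcile Appendix XIII with Section 8.1.8 and Appendices VI and VII for confirmed pregnancy. Align the male-partner wording in Section 8.1.8 with Appendices VI and VII.
- **Aspirin.** Check the 0 to 81 mg entry against the source PDF. If it stands, reconcile the entry, its column and its footnote with the prophylaxis requirement.

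The cost is protocol wording only: a short addendum and a memo to sites. Sample size, analyses and data collection stay as they are.
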